1.7 Termination criteria

- 1) A diagnostic physician at each center will assess the severity of the disease in the study. If the subjects showed the symptoms of facial pain that could not be alleviated by acupuncture (the VAS score > 8 points), the physician will assess the seriousness and terminate the study.
- 2) During the study period, the subjects had serious adverse events such as severe infection, coma, shock, even death and so on, the main investigator should be reported immediately and the study should be terminated immediately.

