1.3 Inclusion criteria

- 1) Paroxysm pain involving branches of the 2nd and/or 3rd branch of trigeminal nerve.
- 2) The visual analogue score(VAS) baseline score ≥ 5 points, have a attack more than 3 times a day, at least 4 days a week.
- 3) 18 years \leq age \leq 80 years.
- 4) Clear consciousness, have the ability of pain perception and resolution, can complete the basic communication.
- 5) Signed informed consent and volunteered to participate in this study.

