1.5 Removed criteria

The subjects who have entered a group of research but who were met one of the following conditions should be removed:

- 1) Those who do not meet exactly with the inclusion and exclusion criteria of the trial.
- 2) There are obviously adverse reactions during the treatment.

3) The subjects are not treated according to the treatment plan of the group after they have entered.

The removed cases should indicate the reason and retained the original medical records. No participation of statistical analysis of efficacy, but those who have received at least one treatment can participate in analysis of adverse reaction.

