1.6 Shedding criteria

Cases that have been entered but not completed the treatment program should be considered as falling off, Such as the following situations:

- 1) Patient withdraws or has been lost their visit.
- 2) The acupuncture treatment has not reached 80%.
- 3) In the treatment, there are serious adverse reactions or adverse events.

The shedding cases should explain the reasons. If the case has been recorded the baseline data, and received at least one time acupuncture treatment, the results of its final main outcome can be carried out for statistical analysis. The medical records should be retained, while the data should not be carried forward during the follow-up.

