disinfection of the facial skin. The superficial acupuncture will be applied for local points. The tiny needles (0.18×25 mm) will be selected to stimulate the local points with shallow row needling according to the distribution of neuropathy branch of trigeminal neuralgia. The technique should be lightly, the depth should be within 5 mm. It is not required a sense of “Qi” and should not touch the trigger point (the trigger points are the pain sensitive places that light touch can trigger severe pain, such as tiff, cheek, nose and so on. The doctor should have a communication with the subject before needling to clear the position of the trigger, do not needle or touch it.) The He-gu (LI4) and Wai-guan (SJ5) points will be selected as the distal points stimulating with 0.25×40mm needle (20-30mm depth). After the subject has a sense of acid distention (“get Qi”), the reducing method of twirling and lifting-inserting will be applied 10 times. If the subject is feeling pain seriously, the distal acupoints can be needling firstly with reducing method sharply until the pain relief. Then it’s turn to needling the local acupoints .

EA parameters: The Xia-guan (ST7) and Quan-liao (SL18) (or Xia-guan (ST7) and Jia-che (ST6)), He-gu (LI4) and Wai-guan (SJ5) acupoints will be received EA treatment by HuaTuo SDZ- II B acupoint neural stimulator. The EA parameter is a dilute wave with 2/100 Hz, the treatment time is 60 minutes and the current intensity is comfortable to subjects.

4) Oral carbamazepine

Carbamazepine tablets (Jiangsu Pengli Pharmaceutical CO., LTD., 0.1g*100 tablets) should be took orally, 0.1g each time, thrice daily.

5) Frequency, duration and time

Treatment will be performed 3 times per week, and 4 weeks of continuous interventions for a total of 12 times.

(2) EA + Placebo group

In this group, the selection, positioning and manipulation of acupoints, the frequency, duration and retaining needle time of treatment are same as EA + Carbamazepine group; placebo, that appearance and specifications are the same as

carbamazepine, are cooperated taken of dose 0.1g, thrice daily.

(3) Sham EA+ Carbamazepine group

Selection of points and locations: the non-meridional points which are means to the points beside 5-10mm of the real acupoints (avoid the trigger point) in the EA group will be selected and needled with more shallow acupuncture (the depth of needling is about 1-2mm).

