2.5 Emergency treatment

It is forbidden that another analgesic therapies are applied at any time during the trial except the patients continue not pain relief, and seriously affect the daily work and life, can use emergency (add) carbamazepine tablets 0.2 g, once time a day, after a meal. The use date and time and dosage of emergency drugs or other analgesic measures must be recorded in time.

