2.6 Therapeutic effects indexes

Subjects are required to write a verifiable diary card to record their pain symptoms in 24 hours every day. The diary includes the following items: (1) daily attack frequency (spontaneous and provoking pain frequency); (2) provoking factors; (3) average pain intensity(VAS) in the past 24 hours; (4) side effect in the past 24 hours (including side effect of drugs or acupuncture); (5) Is there another analgesia therapies have been adopt ? Please record it.

(1) Indexes of main outcome evaluation

- 1) Change from Baseline Intensity of Pain at 6 months (evaluation of the pain by VAS with 0-10 points).
- 2) Change from Baseline Brief introduction of 2-week pain.

Evaluation method: According to pain diary, we will take average data of 2 weeks before treatment (-2~0 week) as baseline, 2 weeks of treatment phase (1~2 week) as data of treatment phase I, 4 weeks of treatment phase (3~4 week) as data of treatment phase II. During the follow-up period, the pain diary card will be continued in the 2 weeks before 3 months (11~12 week)/6 months (23~24 week) after treatments.

(2) Indexes of secondary outcome evaluation

- 1) Brief Pain Inventory-Facial scale (BPI-Facial)
- 2) Patient Global Impression of Change (PGIC)
- 3) Short-Form McGill Pain Questionnaire
- 4) Short- Form 36 Questionnaire

(3) Research cycle and evaluation time points

The treatment periods of this research are 4 weeks, and the follow-up period is 6 months. The above indexes are observed at the time points of baseline (the same day with the grouping and treatment for the subject), treatment period I (the end of the 2nd week), treatment period II (the end of the 4th week), follow-up period I (3rd months after treatment) and follow-up period II (6th months after treatment). The main outcome indexes will be measured weekly (1th week to 4th weeks) during the treatment period.

(4) Safety evaluation and acupuncture expectation evaluation

The relevant safety indicators during the treatment period and during the follow-up period are recorded at any time on the subjects' adverse event records, which is recorded by the acupuncture physician.

- 1) Safety evaluation of electric needle:

The abnormal acupuncture should be record, including broken needle, left needle, fainting, unbearable acupuncture pain (VAS \geq 8 points), local hematoma, infection and abscess. And the symptoms, average degree and average duration of other discomfort

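### Stopping a subject for unrelieved pain (VAS > 8) can remove the 6-month VAS because pain was high, and the protocol and SAP give conflicting rules for the gap

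*Combined protocol and SAP*

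**What the plan says.** Protocol section 1.7 item 1 deals with facial "pain that could not be alleviated by acupuncture (the VAS score > 8 points), the physician will assess the seriousness and terminate the study". It does not say whether the VAS reading is momentary, worst or average, or whether rescue comes first. Section 2.5 allows extra carbamazepine as an exception to the ban on other analgesics: "except the patients continue not pain relief, and seriously affect the daily work and life".

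Entry under section 1.3 requires "The visual analogue score(VAS) baseline score" of at least 5, with no upper limit. The first main outcome in section 2.6 is "Change from Baseline Intensity of Pain at 6 months", on a 0-10 VAS.

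Three places bear on the data of a stopped patient:

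- Protocol section 1.6 covers anyone who entered but did not complete treatment, including those below 80% of acupuncture sessions. After baseline and at least one session, "the results of its final main outcome can be carried out for statistical analysis", yet "the data should not be carried forward during the follow-up".
- SAP section 2.1 puts every randomised patient with at least one treatment in the FAS and fills missing main-outcome values by LOCF. The PPS requires the main outcome to have been evaluated.
- Protocol section 1.5 item 3 bars from efficacy analysis cases where "The subjects are not treated according to the treatment plan of the group after they have entered".

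SAP section 2.2 has the main outcome analysed by PP and ITT together and does not say which of these rules prevails.

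**The concern.** The event that ends participation is a high value of the variable that the trial measures. If follow-up then stops, loss of the 6-month VAS is related to the outcome and is probably more frequent in arms with more pain. One arm receives sham EA plus placebo, so unequal loss is plausible.

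The same patient may then be left missing or be given a last, high value to stand for month 6, depending on which section the analyst follows. Unless one rule is fixed beforehand, it could be chosen after results are seen.

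**Working it through.** **Which rule reaches a stopped patient.** Section 2.4 plans "4 weeks of continuous interventions for a total of 12 times", three per week. The 80% limit is 0.80 × 12 = 9.6 sessions. A patient stopped at the end of week 2 has had 3 × 2 = 6 sessions; at the end of week 3, 3 × 3 = 9. Both are below 9.6, so section 1.6 applies. SAP section 2.1 also applies, because the patient was randomised and treated.

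The section 1.6 sentence on carrying forward can be read in two ways:

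- If it means that values are not imputed, it contradicts LOCF in the SAP.
- If it means that data collection does not continue, it confirms that the 6-month value is lost.

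A patient stopped on a week-4 reading may have had all 12 sessions. Section 1.6 then applies less clearly, but the 6-month value can still be lost.

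**Size.** The documents give no termination rate, so there is no plan figure to reproduce. What follows is an illustration.

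- From the documents: entry VAS at least 5, 0-10 scale, threshold above 8, and SD 1.6 (the planning SD in section 2.1, not a documented baseline SD).
- Assumed: entry mean 7, correlation 0.4 between any two readings, mean falls of 0.5 (control) and 1.5 (treated), two generic arms, no rescue.

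Benefit = mean fall in the treated arm minus mean fall in the control arm at month 6. With full data it is 0.99. Simulation with 400,000 patients per arm:

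| Who is stopped | Lost, control / treated | Of 30 | Benefit, left out | Benefit, LOCF | Gap |
|---|---|---|---|---|---|
| Strict: > 8 at weeks 2 and 4, week 4 not below entry | 4.4% / 0.6% | 1.3 / 0.2 | 0.97 | 1.04 | 0.07 |
| > 8 at week 2 or 4 and not below entry, half stopped | 12.0% / 3.8% | 3.6 / 1.1 | 0.95 | 1.11 | 0.16 |
| As above, all stopped | 24.0% / 7.5% | 7.2 / 2.3 | 0.90 | 1.22 | 0.32 |

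Against 0.99, leaving patients out moves the benefit by 0.02, 0.04 and 0.09. LOCF moves it by 0.05, 0.12 and 0.23 the other way. At correlation 0.7 the gap is about 0.1 (half stopped) and 0.2 (all stopped).

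A different model gives a larger gap. With control treatment-phase mean 6.5, everyone above 8 stopped and a true benefit of 1.0, about 17% and 6% are lost. Leaving out then gives 0.79 to 0.91 and LOCF 1.18 to 1.27, a gap of nearly 0.4. The assumptions set the size.

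**Effect of treatment after stopping.** Suppose stopped patients gain a further r points from other care. The benefit that follow-up would observe is 0.99 − r × (control loss − treated loss).

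- Half stopped: r = 0.5 gives 0.99 − 0.5 × 0.082 = 0.95; r = 1.0 gives 0.91. Leaving out gives 0.95.
- All stopped: r = 0.5 gives 0.99 − 0.5 × 0.165 = 0.91; r = 1.0 gives about 0.82. Leaving out gives 0.90.

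At about half a point of relief the completer bias vanishes. Beyond that it reverses, and leaving patients out overstates the benefit, as LOCF does.

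**Scale.** If SD 1.6 applies to change (assumption), the standard error of a 30 v 30 comparison is 1.6 × √(2/30) = 0.41. For a 60 v 60 factorial main effect it is 1.6 × √(2/60) = 0.29.

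**The case against.** The strongest reply is that the loss is inferred from silence and an awkward translation. Section 1.7 may mean only that treatment stops. Section 2.6 schedules the 3- and 6-month assessments without exempting anyone, and section 1.6 lets a non-completer's final main outcome be analysed. Physician judgement and rescue carbamazepine would also reduce the number stopped. Every shift from the full-data value in the table is below one standard error, and the two simulated arms are not mapped to the four-arm factorial. Divergence between PP and ITT is what running both is meant to show.

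Most of this stands as a limit on size. It does not settle the conflict between section 1.6 and SAP section 2.1, which rests on stated rules and needs no simulation. Nor does it supply the missing statement that assessment continues.

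Some stronger readings are tempting but not supported:

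- A reader might infer that one patient above 8 ends the whole trial. With entry from 5 and no upper limit, that is implausible.
- A reader might infer that section 1.5 item 3 excludes these patients outright. It reaches them only arguably, because a patient stopped under section 1.7 was handled as the protocol prescribes.
- A reader might count any reading above 8 up to month 3. The trigger concerns pain not relieved by acupuncture, and acupuncture ends at week 4.

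**Conclusion.** The point holds as a gap in follow-up together with a conflict of rules. A subject can be stopped on a high value of the outcome variable, nothing says that assessment continues, and the protocol and SAP then treat the same non-completer incompatibly. The conflict reaches every non-completer, not only those stopped for pain.

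The size cannot be derived from the documents. Under the main assumed inputs the strict reading shifts the difference by under 0.1 point. With half or all eligible patients stopped, the gap between leaving out and LOCF is about 0.15 to 0.3 points. These figures rest on assumed means, correlation, falls and stopping shares, without rescue.

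A reader might infer a known bias, with PP and ITT pulling in opposite directions. The documents do not support that: the completer direction depends on pain treatment after stopping. The change is worth making because it is cheap and removes a choice from the analysis stage, not because a large bias has been shown.

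**What to change.** - **Protocol section 1.7 item 1:** replace ending the study with stopping study treatment. State whether this covers both EA or sham EA and the blinded tablets, with rescue or other care at the physician's judgement. The clinical threshold stays with the sponsor.
- **Follow-up:** continue the diary and the scheduled 3- and 6-month assessments in patients who agree.
- **Protocol section 1.6:** delete or limit the sentence against carrying data forward, so that observed values are used in the FAS and the SAP section 2.1 rule applies only to values still missing. Without this, patients who decline follow-up meet the same conflict.
- **Protocol section 1.5:** state that these patients stay in the FAS.

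Cost: a protocol amendment and a few extra contacts at visits already scheduled. Some patients will decline. Later values will reflect other pain treatment, which diary item 5 in section 2.6 already records.

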1.8 Clinical ethics and clinical trial registration

The ethics of two hospitals were approved before the trial beginning, and the clinical trials should be registered.

2. Study methods

2.1 Sample size estimation

The glmpower process of SAS9.3 software is applied to estimate the sample size. According to the literature and the preliminary experiment, the mean values of the

VAS score of EA+Carbamazepine group, EA+Placebo group, sham EA+Carbamazepine group, sham EA+Placebo group were 5.23,4.45,5.50,0.00. The standard deviation was 1.6. Under the condition of $\alpha=0.05$, the test efficiency $1-\beta=0.8$, the four groups were allocated with the 1:1:1:1 proportion, the sample size of each group was calculated at least 24. Considering the existence of shedding and other factors, in the premise of guaranteeing the minimum sample size, the sample size was enlarged by 20% to 30 cases in one group, in total 120 cases for 4 groups. Because of the complexity of the sample calculation process of factorial design, the formula is not listed here.

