ID: 2018ZY008-CTN

Research name:

*Electroacupuncture Therapy for Change of Pain in
Classical Trigeminal Neuralgia*

Date: June 20, 2018

Electroacupuncture Therapy for Change of Pain in Classical Trigeminal Neuralgia

Study Protocol

Part1. Study objectives

1. To observe the therapeutic effect and safety of electroacupuncture (EA) in the treatment of classical trigeminal neuralgia (CTN).
2. To evaluate whether EA has the advantage over carbamazepine in the immediate effect, long-term effect and post effect of the analgesia in CTN.
3. To demonstrate whether EA has a synergistic effect with carbamazepine on the treatment of CTN, or even whether EA has an alternative effect on carbamazepine.
4. To establish a standardized, effective and convenient therapy program of EA to promote it widely.

Part2. Study program

1. Study subjects

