2.1 Analysis data set

(1) Full Analysis Set (FAS):

A collection of all randomly assigned and at least one treated case. When analyzing the main therapeutic indicators, the missing values in the FAS set were

transferred to the current (LOCF) method by using the results observed at the latest time point. The Available Case Analysis principle was used in the Analysis of secondary efficacy indicators, general conditions and safety Analysis.

(2) Per Protocol Set (PPS):

Compliance set refers to meet the inclusion criteria and follow the test protocol to complete the treatment of the set of cases, which is consistent with the test protocol, compliance, did not take prohibited drugs, to complete the evaluation of effectiveness (at least the main outcome) cases.

(3) Security Analysis System (SAS):

At least one treatment is received and the actual data of the safety indicator evaluation record is available.

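### The 24 per group cannot be reproduced from the stated means and SD, and the plan does not say which effect it powers

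*Combined protocol and SAP*

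**What the plan says.** Protocol Part 2, section 2.1 (Sample size estimation) describes a SAS GLMPOWER calculation for a 2x2 factorial design with equal allocation. The planning values are called VAS scores and are attributed in general terms to the literature and a preliminary experiment. In the order EA+carbamazepine, EA+placebo, sham EA+carbamazepine, sham EA+placebo, they end: "sham EA+Placebo group were 5.23,4.45,5.50,0.00. The standard deviation was 1.6". At alpha 0.05 and 80% power, "the sample size of each group was calculated at least 24". A 20% allowance raises this to 30 per group, 120 in all. On the method the section says only: "Because of the complexity of the sample calculation process of factorial design, the formula is not listed here".

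Other parts of the document bear on how to read this:

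- Part 1 sets several questions. Objective 2 is "To evaluate whether EA has the advantage over carbamazepine", and objective 3 is "To demonstrate whether EA has a synergistic effect with carbamazepine on the treatment of CTN".
- Section 1.3 admits only patients with a VAS "baseline score ≥ 5 points".
- Section 2.6 gives the first main outcome as "Change from Baseline Intensity of Pain at 6 months".
- SAP 2.1 defines the full analysis set as "A collection of all randomly assigned and at least one treated case", so the number analysed per group could lie anywhere from about 24 to 30.
- SAP 2.2 and 2.3 ask for centre and baseline to be considered and list analysis of covariance among generic tests. They name no factorial effect or primary contrast.

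**The concern.** All the numerical inputs are printed, so the result should be recoverable for some test. A 2x2 design offers two main effects, an interaction, an overall F test and six pairwise comparisons. The required size differs greatly between them. If the effect is not named, a reader cannot tell which conclusion the 80% protects.

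The fourth mean adds to the difficulty. Read as labelled, a VAS score of 0.00 means that patients given sham EA and placebo end pain-free, although they enter at 5 or more. Read as a reduction, 0.00 is possible, but it assumes no sham or placebo response, and the text does not say that the figures are reductions. Every large factorial effect in the calculation comes from this one value.

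This is the only power statement in the documents. A reader who takes the 80% to apply to EA versus carbamazepine, or to synergy, could misread a null result.

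**Working it through.** **Inputs.** Means 5.23, 4.45, 5.50 and 0.00, SD 1.6, alpha 0.05, power 0.80 and equal groups (protocol 2.1); two-sided tests (SAP 2.3).

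**Formulas.** Let n be the number per group, with error df = 4(n-1) and SD² = 2.56.

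- Contrast: λ = n·ψ²/(SD²·Σc²). Σc² is 1 for a main effect (weights ±½), 4 for the interaction and 2 for a pair.
- Overall F (3 df): λ = n·Σ(mean - grand mean)²/SD².
- Power is the probability that the noncentral F with this λ exceeds the 5% critical value.

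**Effects on the printed means.**

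- EA main effect: (5.23+4.45)/2 - (5.50+0.00)/2 = 4.84 - 2.75 = 2.09
- Carbamazepine main effect: (5.23+5.50)/2 - (4.45+0.00)/2 = 5.365 - 2.225 = 3.14
- Interaction: 5.23 - 4.45 - 5.50 + 0.00 = -4.72
- EA alone versus carbamazepine alone: 4.45 - 5.50 = -1.05
- Overall: grand mean 3.795, sum of squared deviations 19.80

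**Attempt to reproduce 24 per group.**

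| Test | Smallest n | λ at that n | Power | Power at n-1 |
|---|---|---|---|---|
| EA main effect | 6 | 6×2.09²/2.56 = 10.24 | 0.861 | 0.783 |
| Carbamazepine main effect | 3 | 3×3.14²/2.56 = 11.55 | 0.844 | 0.557 |
| Interaction | 5 | 5×4.72²/(4×2.56) = 10.88 | 0.872 | 0.773 |
| Overall F | 3 | 3×19.80/2.56 = 23.20 | 0.895 | 0.518 |
| EA vs carbamazepine | 37 | 37×1.05²/(2×2.56) = 7.97 | 0.801 | 0.790 |

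The other pairs need 3 (any comparison with the 0.00 group), 67 (difference 0.78) or 552 (difference 0.27). One-sided tests, alpha of 0.05/3 or 0.05/6, and 90% power were also tried for the contrasts. Nothing fell between 22 and 26. Keeping the means and changing the SD does not help unless it is far larger: 24 per group would need an SD of 3.62 (EA), 5.43 (carbamazepine), 4.08 (interaction) or 6.46 (overall F). The dropout step does reproduce: 24/(1-0.20) = 30.

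**Dependence on the fourth mean.** At 24 per group and 0.00, both main effects, the interaction and the overall F all exceed 99% power. This holds for a fourth mean up to about 1.35, where the EA main effect reaches 0.990. Power falls as the fourth mean nears the other three. At an assumed 5.00, the required n per group is 121 (EA), 50 (carbamazepine), 1026 (interaction) and 48 (overall F).

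**Fourth means that would give 24 (assumed values).** Overall F: 4.12-4.15 or 5.97-6.00. EA: about 2.3 or 6.03-6.07. Carbamazepine: about 4.4 or 8.13-8.17. Interaction: 2.83-2.87 or about 6.6. As an illustration only, 6.00 gives 0.815 for the overall F at 24 (0.796 at 23). The interaction is then 5.23 - 4.45 - 5.50 + 6.00 = 1.28, with power 49% at 24 and 58% at 30. Separately, 6 per group × 4 = 24 is the total N for the EA main effect on the printed means.

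**EA alone versus carbamazepine alone.** This contrast does not use the fourth mean. At SD 1.6 unadjusted, power is 0.614 at 24 and 0.712 at 30. For 80%, the SD left after adjustment would have to be about 1.28 (24) or 1.44 (30).

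**Detectable with 80% power, SD 1.6, unadjusted, two-sided 0.05, at 24 (30) per group.** Main effect 0.92 (0.83); interaction, twice that, 1.85 (1.65); pairwise, √2 times the main effect, 1.31 (1.17) VAS points. The pairwise 95% CI half-width is t(0.975, 4(n-1))·1.6·√(2/n) = 0.92 (0.82).

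**The case against.** **The trial is large enough on its own inputs.** This stands. Every factorial effect needs 3 to 6 per group on the printed means, so 24 is generous. A reader might infer from the failed arithmetic that the trial is underpowered. The documents do not show that for a main effect, the interaction or the overall F test.

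**The 0.00 may be correct.** This stands too. The main outcome is a change from baseline, and 0.00 is coherent as a reduction. What remains is that section 2.1 calls the values scores and does not say otherwise. Nor are the planning means faulty because they fail to favour EA: objective 2 is to evaluate an advantage, and planning values need not assume one.

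**Perhaps 6.00 was meant, or 24 is a total.** Both are tempting, and neither is supported. No part of the document contains 6.00. Each of four tests yields 24 at two ranges of the fourth mean, so a match is easy to find. A misread digit in the text available here cannot be excluded either. If the source does read 6.00, the 24 reproduces for the overall F test, and what is left is that the tested effect is not named.

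**The 61% is unadjusted and was never claimed as 80%.** Both are true. The SAP plans baseline adjustment but gives no correlation. An assumed baseline correlation of 0.5 leaves an SD of 1.6×√(1-0.25) = 1.39 and power of 74% (83% at 30); 0.6 leaves 1.28 and 80% (88%). The figure therefore limits how the power statement may be read and is not a second arithmetic error.

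**Conclusion.** The concern holds as a defect in the power statement. The figure of 24 per group does not follow from the printed inputs for any test tried: the factorial effects and the overall F need 3 to 6, and EA versus carbamazepine needs 37. The powered effect, scale and time point are not stated. The 0.00 is ambiguous and decisive for the factorial effects, but it is not proven wrong, and the origin of the 24 cannot be settled from the text.

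The result does not establish that 120 patients are too few. With a fourth mean between 0.00 and about 1.35, power at 24 per group is about 99% or more for both main effects and the interaction. It could be much lower if the true planning value lies near the other three. The stated 80% should not be taken to cover objective 2, where power is 61% to 71% for a difference of 1.05 unless adjustment lowers the SD enough.

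These figures assume a common SD of 1.6, normal errors, two-sided alpha 0.05 without multiplicity adjustment, no covariates unless stated, and 24 to 30 analysed per group.

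**What to change.** No patients need to be added.

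1. Confirm or correct the four means, the 0.00 above all, and the SD. State their source, whether they are end scores or reductions, the time point, and whether the SD is baseline-adjusted.
2. Name the effect that is powered, and say whether 24 is per group or in total.
3. Rerun the calculation and restate the figure, with the program code in place of the remark about complexity.
4. Add what the trial can detect, for example: with 24 evaluable patients per group (30 if none is lost), SD 1.6 without covariate adjustment and two-sided alpha 0.05, there is 80% power for a main effect of 0.92 (0.83), an interaction of 1.85 (1.65) or a pairwise difference of 1.31 (1.17) VAS points. Recompute these if the SD changes.
5. Report EA alone versus carbamazepine alone with a 95% confidence interval.

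The cost is a check of the inputs, one rerun, one rewritten paragraph and one reported interval. The downside is that the stated power may look less favourable for objective 2 and, depending on the confirmed fourth mean, for the interaction.
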